9.7.2. AF disease score

Probable AF will be estimated using AF disease score with a logistic regression model to predict AF diagnosis among subjects without history of rheumatic valve disease or valve replacement, or other probable indications, using variables defined above (see disease definition). This model will be secondary applied to subjects without AF diagnosis, and the threshold for probable AF will be defined with specificity greater than 65%.

9.7.3. Propensity score

The probability to be treated by rivaroxaban or VKA, as well as rivaroxaban or dabigatran will be estimated with hdPS at index date (Schneeweiss 2009, Rassen 2012). The hdPS will be estimated using a logistic regression model with a large set of variables at index date and three-year history before inclusion, including gender, age, CHA₂DS₂-VASc and HAS-BLED scores. The subjects without correspondence between both hdPS distributions will be considered as outliers (two extremities of the hdPS distribution).

9.7.4. Matching

For the rivaroxaban versus VKA comparison, subjects will be matched 1:1 on hdPS and index date within each population (specific and sensitive); For the rivaroxaban versus dabigatran comparison, subjects will be matched 1:1 on high or low DOAC dosage at index date, hdPS and index date within each population (specific and sensitive). The matching will use the logit of the hdPS with calipers of width equal to 0.2 of the standard deviation of the logit of the hdPS (Austin 2011).

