9.3.3. Exposure

Exposure definitions will use the following variables:

- **VKA** will be defined as B01AA ATC code;
- **DOAC** will be defined as B01AF01 ATC code for rivaroxaban and B01AE07 ATC code for dabigatran;
- **DOAC high dosage** will be defined using CIP codes for rivaroxaban 20mg and dabigatran 150mg;
- **DOAC low dosage** will be defined using CIP codes for rivaroxaban 15mg and dabigatran 110mg;
- **Treatment group** will be defined by the first anticoagulant dispensation during the inclusion period, i.e. rivaroxaban high or low dosage, dabigatran high or low dosage, or VKA;
- **Index date** will be defined as the date of the first dispensation of the anticoagulant in the treatment group;
- **Duration of a drug dispensation** will be defined as the number of daily doses for DOAC and 30 days for VKA;
- **Drug (DOAC or VKA) exposure** will be defined as the period starting at the index date and ending at the date of the last drug dispensation plus the duration of the last drug dispensation for subject with a drug discontinuation (defined below) or at the date of drug switch (defined below), or at the end of follow-up, whichever is the earliest;
- **Drug (DOAC or VKA) discontinuation** will be defined with a grace period of 60 days for the main analysis and 30 days for a sensitive analysis after the last dispensation plus the duration of the last drug dispensation;
- **Drug (DOAC or VKA) switch** defined as a dispensation of another anticoagulant, including heparin and LMWH dispensation (B01AB ATC code), for subject with a drug discontinuation;
- **Post drug (DOAC or VKA) exposure** will be defined as the period starting at date of the end of drug exposure (see above) and ending at the date a new prescription of an anticoagulant or at the end of follow-up, whichever is the earliest;
- **DOAC compliance** will be estimated using Medication Possession Ratio (MPR) during drug exposure defined by the number of defined daily doses dispensed, divided by the number of days of drug exposure for DOAC. Considering the variable dosage of VKA between subjects and over time in individual subjects, no defined daily dose can be defined, and therefore no MPR for VKA exposure.
- During a hospitalisation, drugs are provided by the hospital, and this time will be taken into account for calculation of drug exposure and drug discontinuation.

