9.3.5. Potential confounding

The potential confounders considered will be:

- **Gender and age** at index date;
- **CHA₂DS₂-VASc score** (Lip GY 2010) at index date, modified to take into account the availability of information in the database, and defined as the sum of points from following stroke risk factors: congestive heart failure (+1), hypertension (+1), age ≥ 75 years (+2), diabetes mellitus (+1), stroke or transient ischemic attack (TIA) history (+2), vascular disease history (+1), age 65-74 years (+1), female gender (+1), within tree-year database history;
- **CHADS₂ score** (for descriptive analysis, Waterman 2001) at index date, modified to take into account the availability of information in the database, and defined as the sum of points from following stroke risk factors: congestive heart failure (+1), hypertension (+1), age ≥ 75 years (+1), diabetes mellitus (+1), stroke or transient ischemic attack history (+2);
- **HAS-BLED score** (Pisters 2010, Lip GY 2011), modified to take into account the availability of information in the database, and defined as the sum of points from bleeding risk factors: hypertension (+1), abnormal renal function (+1), abnormal liver function (+1), stroke history (+1), bleeding history (+1), age > 65 years (+1), drug predisposing to bleeding (+1), within tree-year database history;

- **High dimensional Propensity Scores (hdPS)**: the probability to be treated by one of the studied drugs (rivaroxaban versus VKA, rivaroxaban versus dabigatran), will be estimated using hdPS taking into account all information of the database, with multiple data dimensions from subjects and disease characteristics, other LTD, other comorbidities using one-year history of hospitalisation (primary, linked, or associated diagnosis), three-year history of number of systemic drugs dispensed by therapeutic class (ATC 3 digit, including antacids A02A and drugs for peptic ulcer A02B) and of healthcare reimbursements (number of GP visits, specialist visits, emergency room visits, days of hospitalisation, nurse care and lab tests).
- **Drug predisposing to bleeding** during drug exposure: ASA, NSAIDs, antiplatelet agent and heparin or LMWH.

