9.7.1. Outcomes

Outcomes will be analysed using survival methods for the first occurrence of each outcome:

- Estimation of the one-year and two-year cumulative incidence of each outcome, and according to individual diagnose of each outcome, during drug exposure for rivaroxaban, dabigatran, and VKA, using Kaplan-Meier estimate for death and cumulative incidence function for clinical outcomes, in order to take into account death as a competing risk.
- Estimation of the incidence rate (per 100 PY exposed) of each outcome, and according to individual diagnose of each outcome, during drug exposure or if the risk is not constant over the time, during periods with a constant risk.
- Comparison of the one-year and two-year risk of each outcome during drug exposure, rivaroxaban versus VKA, and rivaroxaban versus dabigatran, using Cox proportional hazard risk model (Cox 1972) for death and Fine and Gray model (Fine 1999) for clinical outcomes, in order to take into account death as a competing risk. Hazard ratio will presented as a point estimate with its 95% confidence interval.
 - Main analysis will compare the incidence of each outcome for matched subjects with time dependant variables adjustment for drug predisposing to bleeding during drug exposure (time dependant variable),
 - Secondary analysis will compare the incidence of each outcome with all subjects, except outliers, with adjustment for hdPS and drug predisposing to bleeding during drug exposure (time dependant variable) for the rivaroxaban versus VKA comparison; and plus low or high DOAC dosage at index date for the rivaroxaban versus dabigatran comparison.
 - Prognostic analysis will be done with all subjects, but outliers, to assess outcome risk factors, including gender, age, CHA₂DS₂-VASc and HAS-BLED scores, low or high dosage at index date for DOAC, drug predisposing to bleeding during drug exposure (time dependant variable) and significant baseline characteristics. The significant baseline characteristics will be identified firstly with univariate analyses, and therefore using a forward stepwise (taking into account the size of the database, the p threshold will be set at 1/1000 for variables selection and at 5% for the stepwise procedure).

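### The rivaroxaban-dabigatran hdPS is worded as a model of drug choice without index dose, yet pairs are matched exactly on dose, so balance within dose is not guaranteed and the head-to-head result may be biased

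*Protocol*

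**What the plan says.** - **Score.** Section 9.3.5 describes the hdPS as "the probability to be treated by one of the studied drugs (rivaroxaban versus VKA, rivaroxaban versus dabigatran"). Section 9.7.3 adds "The hdPS will be estimated using a logistic regression model with a large set of variables at index date and three-year history before inclusion", naming gender, age and the two risk scores. Index dose is neither listed nor expressly excluded.
- **Matching.** Section 9.7.4 adds dose as a separate factor for this comparison: "subjects will be matched 1:1 on high or low DOAC dosage at index date, hdPS and index date within each population (specific and sensitive"). It gives a single caliper rule, "calipers of width equal to 0.2 of the standard deviation of the logit of the hdPS".
- **Secondary analysis.** The section headed Outcomes (the second one numbered 9.7.1) adjusts all subjects for the hdPS "plus low or high DOAC dosage at index date for the rivaroxaban versus dabigatran comparison".
- **Dose as part of treatment.** Section 9.3.3 defines the treatment groups as "rivaroxaban high or low dosage, dabigatran high or low dosage, or VKA". Dose is therefore chosen with the drug and is not a pre-treatment covariate.
- **Safeguards.** Section 9.7.5 plans standardised differences for each comparison. It does not say by dose level, and it states no action if imbalance is found. The main outcome model adjusts matched subjects only for time-dependent use of drugs that raise bleeding risk. The sensitivity analyses in 9.7.1 (Generalities) vary the grace period, the NVAF definition and the classification of unspecified bleeding, but not the score.

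**The concern.** A propensity score for drug choice makes the two drug groups comparable among patients with the same score. Requiring each pair also to share a dose level adds a condition that the score was not built for. Suppose low dose is used more readily with one drug, and that age drives dose. The low-dose group on that drug then takes in relatively younger patients, and its high-dose group keeps only the youngest. At a given score, the other drug's patients are older in both dose strata. The two errors have the same sign and add up when the pairs are pooled.

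This comparison is one of the two in the main objective (section 8). Its main model contains nothing that would correct a residual imbalance in age or comorbidity.

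**Working it through.** The protocol states no figure on this point, so there is nothing to reproduce. The check is the balancing property itself, followed by simulations under assumed dose rules.

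**1. Balancing property.** Let T = 1 for rivaroxaban and 0 for dabigatran, D = 1 for low dose, X the covariates, e(X) = P(T=1 | X), and p_t(X) = P(D=1 | T=t, X). Matching on e(X) alone gives T independent of X. Matching on e(X) and D needs T independent of X given both. By Bayes' rule:

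- low dose: odds(T=1 | X, D=1) = odds of e(X) × p_1(X)/p_0(X)
- high dose: odds(T=1 | X, D=0) = odds of e(X) × [1−p_1(X)]/[1−p_0(X)]

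The factors are 1 if both drugs follow the same dose rule. If the rules differ, the factors generally vary with X at a fixed e(X), and balance within dose is lost.

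**2. Numbers in the formula (assumed rules, standardised age a).**

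| Rule (logit of low dose) | Stratum | Factor at a = −1 | Factor at a = +1 |
|---|---|---|---|
| Same for both: −0.5 + 1.2a | low / high | 1.00 / 1.00 | 1.00 / 1.00 |
| Rivaroxaban −0.5 + 1.2a, dabigatran 0.3 + 1.2a | low | 0.154/0.289 = 0.53 | 0.668/0.818 = 0.82 |
| as above | high | 0.846/0.711 = 1.19 | 0.332/0.182 = 1.82 |
| Rivaroxaban −0.5 + 0.8a, dabigatran 0.5 + 2a | low | 0.214/0.182 = 1.17 | 0.574/0.924 = 0.62 |
| as above | high | 0.786/0.818 = 0.96 | 0.426/0.076 = 5.61 |

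In the second rule the odds of rivaroxaban rise with age in both strata, so the imbalances add. In the third they rise in high dose and fall in low dose, so they partly cancel.

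**3. Matched simulation.** Inputs: 40,000 subjects; no drug or dose effect; logit of drug choice 0.4 + 0.1a + 0.5w, where w is a second covariate; risk exp(−4 + 0.6a + 0.2w); 1:1 nearest-neighbour matching without replacement, caliper 0.2 SD of the logit; index-date matching left out. Results are the age standardised difference (SMD) and the ratio of expected risk, rivaroxaban to dabigatran. The true ratio is 1.

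| Dose rule (low-dose share, rivaroxaban vs dabigatran) | As worded: SMD, ratio | Score within dose: SMD, ratio |
|---|---|---|
| Same rule (41% vs 39%) | 0.01, 1.02 | 0.00, 1.00 |
| Small frequency gap (41% vs 54%) | 0.13, 1.07 | 0.00, 1.00 |
| Large gap (38% vs 64%) | 0.25, 1.14 | 0.00, 1.00 |
| Large gap, stronger age rule (40% vs 66%) | 0.34, 1.20 | 0.00, 1.00 |
| Age weighted differently by drug (40% vs 56%) | 0.14, 1.08 | 0.00, 1.04 |

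Matching on the same score without forcing dose kept the overall age SMD at 0.01 or less, so the imbalance comes from combining this score with exact dose matching. In the last row the within-dose age SMDs as worded were +0.46 (high) and −0.11 (low). Adding dose to the score only as a main effect left +0.21 and −0.22.

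**4. Other assumptions.** A second simulation (400,000 subjects, age and renal indicators, about 41% low dose on rivaroxaban) gave 1.04, 1.07, 1.10 and 1.13 with 54%, 64%, 74% and 81% low dose on dabigatran. A third, with about 43% versus 52–62%, gave about 1.05–1.08 (SMD 0.09–0.17), the same bias in the hdPS-plus-dose secondary model, and about 1.00 with a dose-stratum score. A two-covariate set with equal dose weights for the two drugs showed almost nothing even at 37% versus 68% (ratio 1.01). With unequal weights, within-dose SMDs reached 0.45 while the pooled SMD stayed at 0.07 or less and the pooled ratio at 0.99.

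**5. Yardstick.** At 20,000 per group, the table in section 9.5 puts the smallest hazard ratio above 1 whose interval excludes 1 at 1.20 for 2% incidence, 1.13 for 4% and 1.12 for 5%.

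**The case against.** The strongest reply is that the defect is inferred. The protocol does not say that dose is left out of the score or that one score is fitted across doses. Section 9.3.5 speaks of using all the information in the database, and section 9.6 leaves decision rules and calculated variables to the SAP, which may contain a dose-specific score. This stands as a limit on the claim. It does not remove it: the protocol fixes what the score predicts and places dose beside it in both the matching and the secondary model, and the natural reading is a score without dose.

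A reader might go further and infer that the matched patients are not balanced and the comparison is biased. The document does not support that. It gives no low-dose shares and nothing to show that dose is chosen differently for the two drugs. With one shared rule there is no material problem. The sizes also depend on the chosen coefficients: at 41% versus 54%, two simulations gave 1.04 and 1.07.

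The planned standardised differences would reveal the case where errors add. Where opposite imbalances cancel in the pooled table, the pooled ratio was close to 1, and the protocol specifies no within-dose hazard ratios. Both points stand. But no action is tied to the table, and in the age-weighting scenario the cancellation was only partial (pooled ratio 1.08).

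Finally, a dose-specific score still conditions on dose. It cannot remove unmeasured determinants of dose, and section 9.9 notes that biological results are lacking. This also stands.

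**Conclusion.** The point holds conditionally. As worded, the score, the exact dose match and the secondary adjustment do not together guarantee balance within dose for rivaroxaban versus dabigatran. The main head-to-head result may be biased if dose choice depends on patient characteristics differently for the two drugs. The protocol does not fix the size: under assumed dose rules it runs from nil to a spurious ratio of roughly 1.04–1.2. The upper part of that range is comparable with the smallest ratios that section 9.5 expects to distinguish from 1 at 20,000 per group and 2–5% incidence.

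The conclusion rests on reading the hdPS as omitting dose, and on simulations with few covariates, all of them measured, and no index-date matching in the main set. It is a worthwhile and cheap improvement to one of the two main comparisons, not a demonstrated bias. The rivaroxaban-VKA comparison is not affected, since it is not matched on dose.

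**What to change.** In 9.7.3 and 9.7.4, state that the rivaroxaban-dabigatran hdPS is estimated separately within the high-dose and low-dose strata, or with dose and its interactions with the covariates. A dose main effect alone is not enough when dose rules weigh covariates differently by drug. Trim outliers and apply the 0.2 SD caliper within stratum, then pool the pairs. Use the same score in the secondary all-subject analysis. In 9.7.5, report standardised differences by dose stratum as well as pooled, and say what follows if they exceed a set limit.

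In 9.9, add that unmeasured determinants of dose remain a limitation. Optionally, add a sensitivity analysis matched on the hdPS without dose, to show how far the result depends on conditioning on dose.

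The cost is protocol and SAP wording, two logistic models instead of one, and possibly slightly fewer pairs. In the simulations, pairs changed from 14,728 to 14,590 with the small frequency gap and from 13,210 to 12,973 with the large one, losses of 138 (0.9%) and 237 (1.8%).

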9.7.5. Population description

The population description will include the following analyses:

- A flow chart depicting the total number of subjects available in the database, those satisfying the cohort criteria according to the treatment group, outliers (if any), and the number of matched subjects for each comparison, and in each cohort;
- Description of baseline characteristics, three-year history previous to inclusion, follow-up duration for all and matched subjects according to the treatment group (rivaroxaban, dabigatran, VKA), with standardised difference for each comparison planned (rivaroxaban versus VKA, and rivaroxaban versus dabigatran).

9.7.6. Drug exposure

Description of drug use patterns including drug MPR for DOAC, dosage, treatment discontinuation, switch to another anticoagulant, co-dispensation of drug predisposing to bleeding, and one-year and two-year treatment maintenance for all and matched subjects according to the treatment group, with standardised difference for each comparison planned (rivaroxaban versus VKA, and rivaroxaban versus dabigatran).

9.7.1. Outcomes

Outcomes will be analysed using survival methods for the first occurrence of each outcome:

- Estimation of the one-year and two-year cumulative incidence of each outcome, and according to individual diagnose of each outcome, during drug exposure for rivaroxaban, dabigatran, and VKA, using Kaplan-Meier estimate for death and cumulative incidence function for clinical outcomes, in order to take into account death as a competing risk.
- Estimation of the incidence rate (per 100 PY exposed) of each outcome, and according to individual diagnose of each outcome, during drug exposure or if the risk is not constant over the time, during periods with a constant risk.
- Comparison of the one-year and two-year risk of each outcome during drug exposure, rivaroxaban versus VKA, and rivaroxaban versus dabigatran, using Cox proportional hazard risk model (Cox 1972) for death and Fine and Gray model (Fine 1999) for clinical outcomes, in order to take into account death as a competing risk. Hazard ratio will presented as a point estimate with its 95% confidence interval.
 - Main analysis will compare the incidence of each outcome for matched subjects with time dependant variables adjustment for drug predisposing to bleeding during drug exposure (time dependant variable),
 - Secondary analysis will compare the incidence of each outcome with all subjects, except outliers, with adjustment for hdPS and drug predisposing to bleeding during drug exposure (time dependant variable) for the rivaroxaban versus VKA comparison; and plus low or high DOAC dosage at index date for the rivaroxaban versus dabigatran comparison.
 - Prognostic analysis will be done with all subjects, but outliers, to assess outcome risk factors, including gender, age, CHA₂DS₂-VASc and HAS-BLED scores, low or high dosage at index date for DOAC, drug predisposing to bleeding during drug exposure (time dependant variable) and significant baseline characteristics. The significant baseline characteristics will be identified firstly with univariate analyses, and therefore using a forward stepwise (taking into account the size of the database, the p threshold will be set at 1/1000 for variables selection and at 5% for the stepwise procedure).
- Estimation of cumulative incidence of each outcome during post-anticoagulant exposure period for rivaroxaban, dabigatran, and VKA (i.e. after anticoagulant discontinuation), using Kaplan-Meier estimate for death, cumulative incidence function for clinical outcomes (stroke and SE, ACS, CRB), in order to take into account death as a competing risk.

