8. RESEARCH QUESTION AND OBJECTIVES

The research question is to assess the one-year and two-year benefit-risk of rivaroxaban for SPAF compared to VKA and dabigatran among new anticoagulant users.

The main study objective is to compare the one-year and two-year risk of each of the following individual outcomes: Stroke and systemic embolism (SE), major bleeding and death between new users of anticoagulant for SPAF during drug exposure: rivaroxaban versus VKA, and rivaroxaban versus dabigatran.

Secondary objectives are:

- To describe the drug exposure to rivaroxaban, dabigatran, and VKA for SPAF in new users, as well as pattern of use;

¹ Agence Nationale de Sécurité du Médicament et des produits de santé (French Medicines Agency)

² Caisse Nationale de l'Assurance Maladie des Travailleurs Salariés (French National Health Insurance Fund for Salaried Workers)

- To compare the one-year and two-year risk of the following individual outcomes: a composite of stroke and SE, major bleeding and death, clinically relevant bleeding (CRB) and acute coronary syndrome (ACS) between new users of anticoagulant for SPAF during drug exposure: rivaroxaban versus VKA, and rivaroxaban versus dabigatran;
- To estimate the cumulative incidence and the incidence rate of each individual main and secondary outcome (stroke and SE, major bleeding, CRB, death, composite criteria, and ACS), as well as according individual diagnose of each of these outcomes, during drug exposure for rivaroxaban, dabigatran, and VKA;
- To estimate the cumulative incidence of each individual main and secondary outcome (stroke and SE, major bleeding, CRB, death, composite criteria, and ACS), as well as according individual diagnose of each of these outcomes during post-anticoagulant exposure for rivaroxaban, dabigatran, and VKA (i.e. after anticoagulant discontinuation);
- To assess outcome risk factors, including (but not limited to), gender, age, stroke and bleeding risk scores (CHA₂DS₂-VASc and HAS-BLED), low or high dosage at index date for DOAC, drug predisposing to bleeding during drug exposure and significant baseline characteristics;
- To describe and compare healthcare resources utilisation related to SPAF during rivaroxaban, dabigatran, and VKA exposure, including outcomes, and their related costs from the societal perspective and from the French healthcare insurance perspective.

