10.1 Does the plan include measurement of excess risks?				28
10.2 Is the choice of statistical techniques described?				26 to 28
10.3 Are descriptive analyses included?				27
10.4 Are stratified analyses included?				26 to 28
10.5 Does the plan describe methods for adjusting for confounding?				26to28-30
10.6 Does the plan describe methods addressing effect modification?				

Comments:

10.6: See item 7.2.

Section 11: Data management and quality control	Yes	No	N/A	Page Number(s)
11.1 Is information provided on the management of missing data?				
11.2 Does the protocol provide information on data storage? (e.g. software and IT environment, database maintenance and anti-fraud protection, archiving)				
11.3 Are methods of quality assurance described?				28-29
11.4 Does the protocol describe possible quality issues related to the data source(s)?				29-30
11.5 Is there a system in place for independent review of study results?				26-31

Comments:

ENCePP Checklist for Study Protocols (Revision 2)

4

11.1: The SNIIRAM (data sources) contains exhaustive information about reimbursed treatments out of hospital and use of reimbursed healthcare resources.

Section 12: Limitations	Yes	No	N/A	Page Number(s)
12.1 Does the protocol discuss: 12.1.1 Selection biases? 12.1.2 Information biases? (e.g. anticipated direction and magnitude of such biases, validation sub-study, use of validation and external data, analytical methods)				29

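### The main objective is one-year and two-year risk and the checklist claims that excess risks are measured, but the only planned between-arm outcome measure is a hazard ratio

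*Protocol*

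**What the plan says.** **Objective (Protocol section 8; same in the abstract).** The research question is the one-year and two-year benefit-risk of rivaroxaban. "The main study objective is to compare the one-year and two-year risk of each of the following individual outcomes", the outcomes being stroke and systemic embolism, major bleeding and death.

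**Analysis (Protocol section 9.7.1 Outcomes, which follows 9.7.6; same in the abstract).**
- Per drug, absolute: "Estimation of the one-year and two-year cumulative incidence of each outcome", by Kaplan-Meier for death and the cumulative incidence function (CIF) otherwise.
- Per drug, rates: "Estimation of the incidence rate (per 100 PY exposed) of each outcome".
- Between arms: the comparison of one-year and two-year risk is made "using Cox proportional hazard risk model (Cox 1972) for death and Fine and Gray model (Fine 1999) for clinical outcomes". The measure reported is "Hazard ratio will presented as a point estimate with its 95% confidence interval".
- The population is named for this comparison: "Main analysis will compare the incidence of each outcome for matched subjects with time dependant variables adjustment" for drugs that predispose to bleeding.

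**Checklist (ENCePP checklist annexed to the Protocol).** Item 10.1, "Does the plan include measurement of excess risks", is ticked Yes with page 28. The table of contents puts section 9.7.1 Outcomes on page 28.

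**The concern.** The target is risk at two fixed horizons, while the planned contrast is a ratio of hazards. A benefit-risk assessment sets strokes avoided against bleeds caused, and that is done in numbers of patients by a given time. Protocol section 7 reports that the health authority asked for the impact on morbidity and mortality in terms of events avoided and adverse effects, which is also an absolute quantity.

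A reader of the final report would have hazard ratios with intervals and a set of per-drug incidences. To obtain an excess risk, the reader would have to subtract one incidence from another. The result would have no interval and, if the incidences are for all subjects and not the matched ones, no control of confounding. The checklist meanwhile tells a regulator that excess risk is measured.

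**Working it through.** **1. Search for an excess-risk measure.** Neither section 9.7.1 Outcomes nor the corresponding part of the abstract names a risk difference, risk ratio, rate difference or number needed to treat or harm. The healthcare resources section, listed on the same page, compares resource use and cost and does not supply one. Checklist item 3.3 lists absolute risk, excess risk and hazard ratio as separate examples of effect measures, so the checklist does not treat a hazard ratio as an excess risk.

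**2. Population of the cumulative incidences.** Sections 9.7.5 (population description), 9.7.6 (drug exposure) and 9.7.2 (healthcare resources and cost) each say that results are given for the full and for the matched groups. The cumulative incidence bullet in 9.7.1 Outcomes names only the three drugs. As written, it can be met with unmatched curves.

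**3. What one hazard ratio means at the two horizons (illustration only; no figure in the Protocol is in dispute).**

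Inputs:
- VKA stroke/systemic embolism rate 1.6 per 100 person-years, 95% CI 1.1 to 2.1 (section 9.5).
- Hazard ratio 0.79, 95% CI 0.66 to 0.96, from the ROCKET AF trial (section 7).

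Formula: risk(t) = 1 - exp(-rate × t); difference = [1 - exp(-rate × HR × t)] - [1 - exp(-rate × t)].

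- One year, reference: 1 - exp(-0.016) = 1.59%. Rivaroxaban: 1 - exp(-0.016 × 0.79) = 1 - exp(-0.01264) = 1.26%. Difference -0.33 points, or -3.3 per 1,000.
- Two years, reference: 1 - exp(-0.032) = 3.15%. Rivaroxaban: 1 - exp(-0.02528) = 2.50%. Difference -0.65 points, or -6.5 per 1,000.

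| Varied input | One year, per 1,000 | Two years, per 1,000 |
|---|---|---|
| Central (1.6; 0.79) | -3.3 | -6.5 |
| Rate 1.1 to 2.1, HR 0.79 | -2.3 to -4.3 | -4.5 to -8.5 |
| Rate 1.6, HR 0.66 to 0.96 | -5.4 to -0.6 | -10.6 to -1.2 |

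The same ratio of 0.79, assumed for death at the Protocol's rate of 3.5 per 100 person-years, would give -7.1 and -13.8 per 1,000. So one hazard ratio corresponds to excess risks that about double between the horizons and differ by outcome.

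**4. Why the interval matters.** With 10,000 per arm (one of the sizes tabulated in section 9.5), no censoring, and matching ignored, the one-year standard error is √[(0.01587 × 0.98413 + 0.01256 × 0.98744)/10,000] = 0.00167. The 95% half-width is 1.96 × 0.00167 = 3.3 per 1,000, as large as the illustrated difference. A bare subtraction would hide this.

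**The case against.** The strongest reply is that the absolute quantities are already planned. One-year and two-year incidences and rates per 100 person-years are to be estimated for every outcome and drug, so only a formal contrast and its interval are missing, and such detail can be left to the statistical analysis plan (SAP). Section 9.7.1 Generalities also places the main analysis in the matched cohorts, which may be meant to cover the curves. The checklist describes itself as a supporting document, and its Yes could loosely refer to the per-drug risks. Much of this stands: the gap is narrow, no planned estimate is biased by it, and a SAP could fill it. What remains is that the Protocol itself names the hazard ratio as the reported comparison and claims an excess-risk measure on a page that holds no between-arm one.

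Three stronger readings are tempting, and the documents do not support them.
- *The Cox and Fine and Gray ratios are on incompatible scales and cannot be weighed together.* All-cause death has no competing event, so a Fine and Gray model for death would coincide with the Cox model. Both ratios act on cumulative incidence through the same complementary log-log link. The time-dependent covariate in the main model does weaken the step from either ratio to an absolute risk.
- *The plan does not answer its question at all.* It does compare the arms, by a valid method, and estimates risk per drug at both horizons.
- *The trial's bleeding ratio of 1.03 can be set against its stroke ratio to show the trade-off here.* That ratio belongs to major plus non-major clinically relevant bleeding at about 14.5% per year. This study's clinically relevant bleeding is hospitalised, at 2.6 per 100 person-years, and is not among the three outcomes of the main objective.

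**Conclusion.** The point holds as an inconsistency between the objective, the checklist and the analysis section. The objective is to "compare the one-year and two-year risk of each of the following individual outcomes" and item 10.1 claims excess risks, yet the only between-arm outcome measure is the hazard ratio, and the per-drug incidences carry no contrast, no interval and no stated matched population. The hazard ratio analysis remains valid; it is incomplete for a benefit-risk reading.

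The illustrated size, about -3.3 per 1,000 at one year and -6.5 at two, rests on constant hazards, no competing death or censoring, and a trial hazard ratio carried over to this population. It shows what the ratio leaves out and does not predict the result. The textual finding does not depend on it. It is worth correcting before analysis.

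**What to change.** In section 9.7.1 Outcomes and the matching part of the abstract, state that the following are reported beside the hazard ratio, in each matched cohort (rivaroxaban versus VKA, rivaroxaban versus dabigatran) and for stroke/systemic embolism, major bleeding and death:
- the one-year and two-year on-treatment cumulative incidence in each arm, by Kaplan-Meier for death and CIF for the other two;
- the between-arm risk difference at each horizon with a 95% confidence interval that allows for the matching.

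Checklist item 10.1 is then correct as ticked. If the sponsor prefers not to add the differences, item 10.1 should be changed and the objective reworded as a comparison of hazards.

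The addition uses estimators already planned and needs no new data. The downside is more reported estimates: 2 comparisons × 3 outcomes × 2 horizons = 12 risk differences in the main population.
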